9.3.4. Outcomes

9.3.4.1. Congenital malformations

The study will define and code congenital malformations using the criteria specified by the CDC MACDP and EUROCAT.^{40,41} A malformation may be described and classified by severity (eg, major malformation), by origin (eg, genetic, environmental exposure), and by organ system (eg, urogenital system or malformations known as congenital heart defects [CHD]). An MCM will be defined as any major structural or chromosomal defect detected in live-born infants, stillbirths/fetal losses ≥ 20 gestational weeks, and elective terminations of any gestational age.⁴⁰ This definition is consistent with, but not restricted to, the CDC MACDP and EUROCAT definitions.

To avoid misattribution of the malformation to the medication, MCMs not associated with medication exposure, such as chromosomal abnormalities, genetic syndromes, prematurity-related conditions in infants born at < 36 gestational weeks (eg, patent ductus arteriosus, patent foramen ovale, inguinal hernias, or undescended testes), and positional effects (eg, hip dislocation due to breech position or abnormal skull shape due to crowding by multiple fetuses), will not be considered MCMs in the statistical analyses comparing MCM prevalence between the internal cohorts.⁴² Given that the registry will also use the CDC's MACDP and EUROCAT as external comparators, the registry will include cases of MCMs not associated with medication exposure in the prevalence calculations for this comparison.

Transient malformations in term infants, whether occurring alone or with other malformations, will be reported in the study, as certain transient malformations may be associated with maternal medication exposure in pregnancy and can vary by age of detection and/or age of resolution (eg, CHDs).⁴³ Lastly, the MACDP only includes minor malformations if they occur in the presence of an MCM. However, as stated in the objectives, major and minor malformations are of interest for this study and both will be reported.

Live-born infants with only positional defects (malformations), infectious conditions, or with biochemical abnormalities will be classified and reported separately. The CDC MACDP has different objectives and reporting needs than this project, so a thoughtful adaptation of their guidelines is appropriate.

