The registry will systematically collect information on major and minor structural malformations, transient malformations in term infants, and chromosomal defects that are apparent at birth and noted through infant age 1 year, including: congenital malformation(s) and details, if noted, type of congenital malformation(s) if applicable, attribution to drug therapy, and other factors that might have contributed to the outcome.

If a congenital malformation is reported, other data of interest can be collected through targeted followup.

PFIZER CONFIDENTIAL

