For comparison with external comparators, the prevalence rates of the outcomes of interest among the rimegepant-exposed participants of the main analysis population will be calculated according to the conventions used by the selected external comparators. For example, for the comparison with MACDP, live births and stillbirths with MCMs (including MCMs not associated with medication exposure) will be included in the numerator, and the denominator will be the number of live births. The MACDP calculates rates by this convention, which increases sensitivity. Likewise, for comparisons with the external cohort of pregnant women without migraine (from the retrospective pregnancy outcomes study), the conventions used to calculate outcome prevalence rates in the internal and external cohort will be aligned.

In addition, "crude" prevalence rates, without limitations and exclusions, may be conducted to avoid restricting the main analysis population (denominator). For example, infants with MCM and/or infants born preterm may be included for the prevalence rate calculation of infant developmental delay.

Outcome	Numerator	Denominator	
Primary Outcome – MCM			
Primary analysis: among live births with 1 st trimester exposure (if applicable for cohort)	Live births with confirmed MCMs (excluding MCMs not associated with medication exposure) among women with pregnancy outcome data and exposure during 1 st trimester (if applicable)	Live births among women with pregnancy outcome data and, if applicable, exposure during 1 st trimester	
Secondary analysis: among all pregnancy outcomes with 1 st trimester exposure (if applicable for cohort)	Live births and fetal losses with confirmed MCMs (excluding MCMs not associated with medication exposure) among women with pregnancy outcome data and, if applicable, exposure during 1 st trimester	Live births and fetal losses among women with pregnancy outcome data and, if applicable, exposure during 1 st trimester	
Secondary analysis: among live births with exposure at any time during pregnancy (if applicable for cohort)	Live births with confirmed MCMs (excluding MCMs not associated with medication exposure) among women with pregnancy outcome data and, if applicable, exposure at any time during pregnancy	Live births among women with pregnancy outcome data and, if applicable, exposure at any time during pregnancy	

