Secondary analysis: among all pregnancy outcomes with exposure at any time during pregnancy (if applicable for cohort)	Live births and fetal losses with confirmed MCMs (excluding MCMs not associated with medication exposure) among women with pregnancy outcome data and, if applicable, exposure at any time during pregnancy	Live births and fetal losses among women with pregnancy outcome data and, if applicable, exposure at any time during pregnancy	

Table 4.	Calculation of Outcome Prevalence
----------	------------------------------------------

PFIZER CONFIDENTIAL

Outcome	Numerator	Denominator
Comparison with external comparator (CDC MACDP)	Live births and stillbirths with confirmed MCMs (including MCMs not associated with medication exposure) among women with pregnancy outcome data and exposure during the 1 st trimester	Live births among women with pregnancy outcome data and exposure during the 1 st trimester
Comparison with external comparator (Pfizer Study C4951006 [formerly BHVN Outcomes Study])	Live births with confirmed MCMs (excluding MCMs not associated with medication exposure) among women with pregnancy outcome data and exposure at any time during pregnancy	Live births among women with pregnancy outcome data and exposure at any time during pregnancy
Comparison with EUROCAT	Live births and stillbirths and TOPFA with confirmed MCMs (including MCMs not associated with medication exposure) among women with pregnancy outcome data and exposure during the 1 st trimester	Live births and stillbirths among women with pregnancy outcome data and exposure during the 1 st trimester
Secondary Outcomes		
Minor congenital malformations	Live births with minor congenital malformations among women with pregnancy outcome data	Live births among women with pregnancy outcome data
Gestational diabetes		
Primary analysis between internal cohorts	Gestational diabetes among women with pregnancy outcome data	Women with pregnancy outcome data
Comparison with external comparator (CDC NVSS)	Gestational diabetes among live births	Live births among women with pregnancy outcome data
Gestational hypertension		
Primary analysis between internal cohorts	Gestational hypertension among women with pregnancy outcome data	Women with pregnancy outcome data
Comparison with external comparator ⁶¹	Gestational hypertension among live births	Live births among women with pregnancy outcome data
Pre-eclampsia		

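### The exclusion of malformations not associated with medication covers major malformations only; the minor-malformation numerator, also compared by relative risk, has no such exclusion

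*Protocol*

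**What the plan says.** Protocol section 9.3.4.1 states the principle and its reason: "To avoid misattribution of the malformation to the medication, MCMs not associated with medication exposure, such as chromosomal abnormalities, genetic syndromes", together with prematurity-related conditions in infants born before 36 weeks and positional effects, "will not be considered MCMs in the statistical analyses comparing MCM prevalence between the internal cohorts". Table 4 in section 9.7.3.3 carries this into the internal MCM rows. The primary row, for example, reads "Live births with confirmed MCMs (excluding MCMs not associated with medication exposure) among women with pregnancy outcome data and exposure during 1 st trimester".

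The minor-malformation row of the same table reads "Live births with minor congenital malformations among women with pregnancy outcome data" and stops there. The outcome-specific restrictions listed above Table 4 do not mention minor malformations.

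Two general rules in section 9.3.4.1 partly reach minor findings:

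- Isolated positional findings: "Live-born infants with only positional defects (malformations), infectious conditions, or with biochemical abnormalities will be classified and reported separately".
- Collection: "The registry will systematically collect information on major and minor structural malformations, transient malformations in term infants, and chromosomal defects", which mentions transient malformations for term infants only.

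Section 9.7.3.1 lists minor congenital malformation among the binary outcomes that get a relative risk with a 95% confidence interval and p-value. Section 9.7 makes p-values for secondary outcomes nominal. Section 9.4.4 has all reported malformations classified by evaluators blinded to exposure, with the same method in both cohorts.

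**The concern.** The reason given for the exclusion, avoiding misattribution, does not depend on whether a malformation is major or minor. A minor anomaly that is part of a chromosomal syndrome says no more about rimegepant than a major one does. Followed literally, the plan drops an infant with a chromosomal syndrome from the MCM numerator and then counts the same infant as a case through its minor anomalies.

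Nothing else in the protocol closes the gap. The sensitivity analysis on chromosomal or genetic malformations (section 9.7.3.7) and the subgroup analysis by preterm status (section 9.7.3.5) are specified for MCM only. Other secondary outcomes are guarded against similar contamination: Table 4 takes infants with MCMs and preterm infants out of the developmental-delay denominator, and SGA infants as well out of the growth-deficiency denominator.

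At stake is how the minor-malformation relative risk is read. Cases unrelated to the drug and equally common in both cohorts move a true increase toward 1, which is the unfavourable direction in a safety study. If the cohorts differ in preterm birth, the accompanying minor findings could move the estimate away from 1. Such a difference is conceivable: section 7.3 reports an association of migraine with preterm birth, and section 9.9 warns that migraine severity may differ between the cohorts.

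**Working it through.** **1. The protocol's own figures.** Table 3 has no row for minor malformations, so there is no stated figure for this outcome. The nearest is MCM power in Table 2. Using the two-proportion normal approximation with pooled variance under the null, two-sided alpha 0.05:

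- 390 per cohort, 3% against 3% × 2.5 = 7.5%: 80.6% (stated 80.6%).
- 390 × 0.9 × 0.9 = 315.9, so 316 per cohort; 3% against 3% × 2.7 = 8.1%: 80.1% (stated 80%).

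Both reproduce. Neither depends on the minor-malformation numerator.

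**2. Which findings the text leaves in the minor-malformation count.**

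| Finding in a live-born infant | Internal MCM comparison | Minor-malformation row |
|---|---|---|
| Part of a chromosomal or genetic syndrome | Excluded | Counted; no rule removes it |
| Prematurity-related, born before 36 weeks | Excluded | Unsettled; the row is silent, and the term-only wording concerns collecting and reporting transient malformations |
| Positional defect only | Excluded | Reported separately |

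**3. Dilution.** Let f be the share of reference-cohort cases unrelated to the drug and equally frequent in both cohorts. Then

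observed RR = f + (1 − f) × true RR.

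If the true RR is 1, the observed RR is 1 for any f. If the true RR is 2.0, f = 10%, 20% and 30% give 1.9, 1.8 and 1.7.

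**4. Power.** Assumed, because the protocol gives none of them for this outcome: total reference rate 6%, true RR 2.0, and f. The 316 per cohort comes from section 9.5.2. Without the exclusion the comparison is 6% against 6% × observed RR. With it, the comparison is 6% × (1 − f) against twice that.

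| f | Rates without exclusion | Power | Rates with exclusion | Power |
|---|---|---|---|---|
| 1% | 6% v 11.94% | 74.4% | 5.94% v 11.88% | 74.7% |
| 2% | 6% v 11.88% | 73.7% | 5.88% v 11.76% | 74.2% |
| 10% | 6% v 11.4% | 67% | 5.4% v 10.8% | 70% |
| 20% | 6% v 10.8% | 59% | 4.8% v 9.6% | 65% |
| 30% | 6% v 10.2% | 49% | 4.2% v 8.4% | 58% |

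The cost of leaving the exclusion out is under one point at f = 1-2%, and about 3, 6 and 9 points at 10%, 20% and 30%.

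**5. Imbalance.** Take the 8.47% preterm reference rate from Table 3. Assume 5% other minor malformations in both cohorts, twice the preterm rate in the exposed cohort, and a prematurity-related minor finding in a share q of preterm infants. With no direct drug effect on malformations,

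RR = (5% + 2 × 8.47% × q) / (5% + 8.47% × q).

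- q = 10%: 6.694% / 5.847% = 1.14.
- q = 30%: 10.082% / 7.541% = 1.34.

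With equal preterm rates the ratio is 1. The example also requires that prematurity-related findings are counted at all, which step 2 shows is open.

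**The case against.** A reader might infer that syndromic and prematurity-related findings are booked as rimegepant outcomes, or that the comparison is distorted as a matter of course. The documents do not support this. The same numerator applies to both cohorts, and the evaluators are blinded to exposure. A null effect therefore stays null unless the cohorts differ in the cause of these findings.

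A reader might also infer that minor findings of prematurity certainly count. The protocol's term-only wording on transient malformations may mean that some of them should not. That wording governs collection and reporting, however, and is not an exclusion from a numerator. The question stays open, which is itself a reason to settle it. Isolated positional defects are already reported separately.

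The size is also open to challenge. The clearest gap is minor anomalies in live-born infants with a syndrome, and nothing in the protocol supports a share as high as 10-30% for these. At 1-2% the effect on power is negligible. This stands.

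Finally, it can be said that an inclusive count is a defensible, sensitive choice for a secondary safety outcome, and that section 9.7 leaves detailed methods to the SAP. The first part is fair, but the protocol gives no reason for treating minor and major malformations differently, and an inclusive count can be kept alongside. The second part carries less weight: Table 4 does state a numerator for this outcome, so this is a fixed definition and not an omitted detail. The SAP would nevertheless be an acceptable place to correct it.

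**Conclusion.** The inconsistency is real but modest. Minor malformations are compared by the same relative-risk methods as MCMs without the exclusion that the protocol considers necessary for MCMs. Minor anomalies within chromosomal or genetic syndromes clearly enter the count in both cohorts; prematurity-related findings before 36 weeks may. The expected consequence is attenuation of a true effect, with a false signal only under a cohort imbalance.

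The magnitude cannot be derived from the protocol. It rests on an assumed 6% rate, true RR of 2.0 and non-drug share, and runs from under one power point (share 1-2%) to about nine (share 30%). The outcome is secondary with nominal p-values, and the primary MCM analysis and the sample size are untouched. The change should be made for consistency and interpretability; it does not threaten the study's main conclusion.

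**What to change.** In section 9.3.4.1 and in the minor-malformation row of Table 4, state that the internal comparison excludes minor malformations not associated with medication exposure, including those in infants with a chromosomal or genetic syndrome and prematurity-related findings in infants born before 36 weeks. Report the all-inclusive count as a sensitivity analysis, parallel to the one that section 9.7.3.7 plans for MCM.

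The cost is a phrase in two places and one additional analysis. The blinded evaluators already review and classify all reported malformations. The downside is a slightly smaller case count in the main comparison.

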9.5.2. Full study

The full study will aim to prospectively enroll a minimum of 390 women with migraine who were exposed to rimegepant during pregnancy or just prior to pregnancy (up to 3 days prior to conception), as well as an internal comparison cohort consisting of 390 women with migraine who were not exposed to rimegepant during pregnancy or just prior to pregnancy (up to 5 product half-lives prior to conception). The target sample size for the registry is based on the primary outcome, MCM, which is also the outcome with the most restrictive denominators and 1 of the lowest prevalence rates in the general population. If all are evaluable for potential MCMs (evaluable being those for whom pregnancy outcome and major/minor congenital malformation assessments are obtained), and assuming an approximate 3% overall population prevalence of MCM, ⁵⁴ at α =0.05, this sample size provides 80% power to detect a 2.5-fold increased risk for overall MCM. Most registry power calculations are performed for overall MCM to detect an increased risk between 2- and less than 3-fold.⁵⁵ A midpoint threshold of a 2.5-fold increased risk was selected for this study. Assumptions for study calculations are consistent with those applied in the retrospective pregnancy outcomes study (NDA 212728, postmarketing requirement 3799-7, Pfizer study C4951006 [formerly BHV3000-403]).

Prospective enrollment can occur only after pregnancy is recognized but while the pregnancy is ongoing. Therefore, early pregnancy losses will not be captured, and a live birth rate higher than that of the general population would be expected. Research shows that approximately 90% of pregnancies enrolled in pregnancy exposure registries result in a live birth.^{56,57} Assuming that 90% of prospectively enrolled pregnancies result in live births and 10% are lost to follow-up,⁵⁸ at α =0.05, the study sample of 390 prospectively enrolled pregnant women in each internal cohort would result in 316 evaluable participants per cohort. Therefore, the study would have 80% power to detect a 2.7-fold increased risk of overall MCM (Table 2).

PFIZER CONFIDENTIAL

Outcome	N per cohort	Reference rate	Relative risk detectable	Power ^b
МСМ	390	3% ^{54,55,59}	2.5	80.6%
МСМ	316 ^a	3% ^{54,55,59}	2.7	80%

Table 2.	Sample Size and Power Estimates for Primary	Outcome, MCM

MCM = major congenital malformation; reference rate = prevalence rate of outcome in general population for pregnant women of any age

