Primary analysis between internal cohorts	Pre-eclampsia among women with pregnancy outcome data	Women with pregnancy outcome data
Eclampsia	·	
Primary analysis between internal cohorts	Eclampsia among women with pregnancy outcome data	Women with pregnancy outcome data
Comparison with external comparator ⁶¹	Eclampsia among live births	Live births among women with pregnancy outcome data
Pre-eclampsia/eclampsia	•	
Primary analysis between internal	Pre-eclampsia or eclampsia among	Women with pregnancy outcome

PFIZER CONFIDENTIAL

Outcome	Numerator	Denominator
cohorts	women with pregnancy outcome data	data
Comparison with external comparator (Pfizer Study C4951006)	Pre-eclampsia or eclampsia among women with pregnancy outcome data	Women with pregnancy outcome data
SAB		
Primary analysis between internal cohorts	SABs among women with pregnancy outcome data who are enrolled (and exposed, if applicable) prior to 20 gestational weeks	Women with pregnancy outcome data who are enrolled (and exposed, if applicable) prior to 20 gestational weeks
Comparison with external comparator (Pfizer Study C4951006)	SABs among women with pregnancy outcome data who are enrolled (and exposed, if applicable) prior to 20 gestational weeks	Women with pregnancy outcome data who are enrolled (and exposed, if applicable) prior to 20 gestational weeks
Stillbirth		
Primary analysis between internal cohorts	Stillbirths among women with pregnancy outcome data	Women with pregnancy outcome data
Comparison with external comparator (CDC NVSS)	Stillbirths among women with pregnancy outcome data	Live births and stillbirths among women with pregnancy outcome data
Comparison with external comparator (Pfizer Study C4951006)	Stillbirths among women with pregnancy outcome data	Women with pregnancy outcome data
Elective termination		
Primary analysis between internal cohorts	Elective terminations among women with pregnancy outcome data	Women with pregnancy outcome data
Comparison with external comparator (CDC Abortion Surveillance System)	Elective terminations among women with pregnancy outcome data	Live births among women with pregnancy outcome data
Comparison with external comparator (Pfizer Study C4951006)	Elective terminations among women with pregnancy outcome data	Women with pregnancy outcome data
TOPFA		
Primary analysis between internal cohorts	TOPFA among women with pregnancy outcome data	Women with pregnancy outcome data

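### The Study C4951006 rows for pre-eclampsia/eclampsia and stillbirth use a denominator that includes pregnancies ending before 20 weeks, whose share may differ between the registry and C4951006

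*Protocol*

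**What the plan says.** Protocol Table 4 (section 9.7.3.3) fixes a numerator and denominator for each comparison. In the C4951006 row for pre-eclampsia/eclampsia the numerator is "Pre-eclampsia or eclampsia among women with pregnancy outcome data" and in the C4951006 row for stillbirth it is "Stillbirths among women with pregnancy outcome data". Both are divided by all women with a known pregnancy outcome, whatever that outcome was and whenever it occurred.

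Sections 9.3.4.2 and 9.3.4.3 place stillbirth at or after 20 gestational weeks and pre-eclampsia after 20 weeks.

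Section 9.5.2 says of the registry that "early pregnancy losses will not be captured, and a live birth rate higher than that of the general population would be expected", and that "approximately 90% of pregnancies enrolled in pregnancy exposure registries result in a live birth". Section 9.9 adds that only SABs after enrollment are captured. Sections 9.2.3 and 9.2.3.2 describe C4951006 as a retrospective study in women without migraine that supplies rates of, among other outcomes, SAB and elective termination.

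On comparability, 9.7.3.3 says that "the conventions used to calculate outcome prevalence rates in the internal and external cohort will be aligned".

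Other rows of Table 4 do handle timing. The NVSS stillbirth row divides by "Live births and stillbirths among women with pregnancy outcome data", the published-source rows for gestational hypertension and eclampsia use live births, and the C4951006 SAB row counts "SABs among women with pregnancy outcome data who are enrolled (and exposed, if applicable) prior to 20 gestational weeks".

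**The concern.** A pregnancy that ends before 20 weeks adds to these two denominators but cannot become a case. That is harmless in a ratio only if both cohorts contain the same share of such pregnancies. The protocol says its own cohort contains unusually few. A retrospective cohort that reports SAB and elective termination plausibly contains more.

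Aligning the calculation convention, as 9.7.3.3 promises, gives both cohorts the same label. It does not equalise the share of women who reach the period at risk. Following the table exactly can therefore give a ratio other than 1 when the drug does nothing.

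C4951006 is the only named non-migraine cohort, and its row is the only external pre-eclampsia comparison in Table 4. Section 9.7.3.2 commits to p-values from exact methods for such comparisons. Because 7.3 already links migraine itself to pre-eclampsia, a denominator artefact in the same direction would be hard to separate from disease or drug.

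**Working it through.** **The plan's own figures.** The protocol gives no figure for the C4951006 comparison. The Table 3 rates used below do reproduce its power entries at 390 per cohort for a 2.5-fold increase: pre-eclampsia 3.4% against 8.5% gives 85.5% (normal approximation), and stillbirth 0.596% against 1.49% gives 12.6% (Fisher's exact). Both match.

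**Inputs.** Registry live-birth share 90% (9.5.2). SAB 13.4%, elective termination 18.6%, stillbirth 0.596% and pre-eclampsia 3.40% (Table 3). Exposed women with an outcome: 390 × 0.90 = 351, using the 10% loss to follow-up in 9.5.2.

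**Assumptions not in the protocol.** C4951006 resembles the Table 3 reference rates; all its terminations precede 20 weeks; the 3.40% and 0.596% risks apply per pregnancy reaching 20 weeks in both cohorts (no drug effect, no migraine effect).

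**Share reaching 20 weeks.**
- Registry: 0.90 / (1 − 0.00596) = 0.905.
- C4951006, SAB only: 1 − 0.134 = 0.866.
- C4951006, SAB plus terminations at 18.6 per 100 live births: live-birth share = (1 − 0.134) / (1 + 0.186 + 0.006) = 0.727; reaching 20 weeks = 0.727 / (1 − 0.00596) = 0.731.
- C4951006, 18.6% read as a share of pregnancies: 1 − 0.134 − 0.186 = 0.680.

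**Ratio with no drug effect** = registry share / C4951006 share. The registry pre-eclampsia rate is 3.40% × 0.905 = 3.08% throughout.

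| C4951006 counts | Share reaching 20 weeks | Ratio | C4951006 pre-eclampsia rate |
|---|---|---|---|
| SAB only | 0.866 | 1.05 | 2.94% |
| SAB + terminations per live birth | 0.731 | 1.24 | 2.48% |
| SAB + terminations per pregnancy | 0.680 | 1.33 | 2.31% |

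Section 7.3 also gives a miscarriage range of 15–20%. SAB only at 20% gives 1.13; 15–20% with terminations per live birth gives 1.26–1.34. In the other direction, a registry live-birth share of 80–85% against SAB only at 13.4% gives 0.93–0.99.

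**False signals of excess pre-eclampsia.** One-sample exact binomial test, two-sided 5%, n = 351, external rate taken as fixed. The protocol does not say which exact test, so two are shown.

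| Ratio | Equal-tailed | Minimum-likelihood |
|---|---|---|
| 1.05 | 2.6% | 2.6% |
| 1.24 | 7.9% | 12.9% |
| 1.33 | 12.9% | 19.8% |

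Without the bias the rate is about 1–3%. For example, when both true rates equal the 2.48% external rate, it is 1.6% equal-tailed and 3.1% minimum-likelihood.

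**Stillbirth.** At 1.24 the rates are 0.540% against 0.436%, and the false-signal rate is 4.3% against 2.0% without the bias. At 1.33 it is still 4.3%. It does not exceed 5%.

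**An opposing effect on stillbirth.** Prospective enrollment is allowed at any time before the outcome (9.3.1.2), including late in pregnancy (9.2). A woman who enrolls after 20 weeks cannot contribute an earlier stillbirth, which lowers the registry rate. If 1 − 1/1.24 = 19% of stillbirths preceded enrollment, a ratio of 1.24 would be cancelled.

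**The case against.** The strongest reply is that the direction and size depend on a study whose entry rule, data source and loss capture are not shown. Listing SAB and elective termination as outcomes shows that C4951006 counts some losses, not that it counts them at general-population level. This stands. A reader might infer that exposed rates will look raised, or that an excess is bound to arise from the denominator alone; the documents do not support either. The ratio is 1.05 if only SAB is counted and could fall slightly below 1.

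The 1.33 figure, and the false-signal rate of up to 20% that goes with it, requires reading 18.6% per pregnancy. Table 4's CDC abortion-surveillance row divides by live births, which favours 1.24. A fixed external rate also overstates false signals somewhat, because C4951006 has sampling error of its own.

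A reader might also infer that stillbirth is affected as much as pre-eclampsia. It is not: the false-signal rate stays below 5%, the NVSS row already uses live births plus stillbirths, and late enrollment pulls the other way. Changing only the stillbirth denominator would remove the upward component and leave the downward one.

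Finally, secondary p-values are nominal (9.7), the C4951006 rates are meant as context (9.9), and missed early losses are disclosed as a limitation (9.9). All true, and this limits the consequence. It does not answer the point: the limitation is not linked to these rows, and Table 4 fixes the denominator rather than leaving it open.

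**Conclusion.** The point holds in a conditional form. The two C4951006 rows use a denominator that is neutral only if both cohorts have the same share of pregnancies reaching 20 weeks, and the protocol's own text gives reason to doubt that. If C4951006 counts early losses more fully, the pre-eclampsia/eclampsia ratio with no drug effect is about 1.05 to 1.24 (1.33 on the less likely reading of the termination rate). False pre-eclampsia signals are then about 3% at 1.05 and 8–13% at 1.24, against about 1–3% without the bias.

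This rests on C4951006 resembling the Table 3 rates, a 90% registry live-birth share, 351 exposed women and a fixed external rate. For stillbirth the consequence is small and the net direction is not established. The comparisons are secondary and nominal, and the primary MCM analysis is untouched. The rows are still worth changing, because a denominator limited to the period at risk does not depend on how many early losses either cohort captures.

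**What to change.** In Table 4:

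- **Pre-eclampsia/eclampsia, C4951006 row:** use pregnancies reaching 20 gestational weeks as the denominator in both cohorts.
- **Stillbirth, C4951006 row:** use live births plus stillbirths in both cohorts, as in the NVSS row, and restrict the registry side to women enrolled before 20 weeks (or match gestational age at entry).
- Request the same tabulations from C4951006, which is the sponsor's own parallel study, and state its entry rule beside the comparison.

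The cost is two table rows, one re-tabulation and smaller denominators. On the protocol's 90% live-birth assumption, the 20-week limit removes roughly a tenth of registry women (1 − 0.905), none of whom could be a case. The enrollment restriction for stillbirth also removes women who enroll after 20 weeks. The protocol does not give that share; matching on gestational age at entry is the alternative if it proves large.
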